EVALUATION PROTOCOL

Mixed method cluster randomised pilot trial of Multi-Systemic Therapy for Child Abuse and Neglect (MST-CAN) versus business as usual for families with at least one child subject to a child protection plan

The University of Kent

Principal investigator: [name]

Pilot trial protocol template (includes a control group)

Evaluating institution: University of Kent

Principal investigator(s): [name]

Project title ¹	Mixed method cluster randomised pilot trial of Multi- Systemic Therapy for Child Abuse and Neglect (MST-CAN) versus business as usual for families with at least one child subject to a child protection plan.			
Developer (Institution)	MST UK & Ireland, South London & Maudsley NHS Foundation Trust			
Evaluator (Institution)	University of Kent			
Principal investigator(s)	[name]			
Evaluation plan author(s)	[name], [name], [name], [name], [name] [name], [name]			
Evaluation setting	Family			
Target group	Families with at least one child, aged 6-17 years subject to a child protection plan.			
Number of participants 3 sites, 4 local authorities, 72 families				

Protocol version history

Version	Date	Reason for revision
1.0 [original]	17/05/24	

Table of contents

STUDY RATIONALE AND BACKGROUND	4
INTERVENTION	
RESEARCH QUESTIONS	1
SUCCESS CRITERIA AND/OR TARGETS	2
PILOT TRIAL DESIGN	3
IMPLEMENTATION AND PROCESS EVALUATION	11
OUTPUTS	15
COST DATA REPORTING AND COLLECTING	15
ETHICS AND REGISTRATION	18
DATA PROTECTION	19
STAKEHOLDERS AND INTERESTS	21
RISKS	21
TIMELINE	21
REFERENCES	22

Study rationale and background

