In the pilot stage of the study, we will report on the proportion of families who are eligible, consent, adhere to MST-CAN, are followed-up at the primary end point, and complete the primary and secondary outcomes. These proportions will be compared with pre-defined criteria to aid decisions regarding the feasibility of a definitive efficacy RCT.

Table 1: Proposed progression criteria

Criteria

Proportion of potential families who are eligible.	70%	50%	40%
Proportion of eligible families who consent.	70%	50%	40%
Proportion of consenting families who adhere.	80%	60%	50%
Proportion following up at month 9.	80%	70%	60%
Proportion with complete primary outcomes.	95%	85%	75%
Proportion with complete secondary outcomes.	80%	70%	60%

In addition to proportions we will assess data completeness for each outcome instrument. A threshold of 60% complete will be used to assess whether an outcome instrument should be included in any future efficacy trial.

Methods

Pilot trial design

Two-arm, mixed method cluster randomised controlled trial comparing MST-CAN versus BAU across three sites (four local authorities) in England and Wales. The unit of randomisation will be the family.

Randomisation

Randomisation will employ random permuted blocks of variable size stratified by geographical site, Wrexham and Flintshire, Sandwell and Leeds. Random strings will be created for each site and deployed independent of the research team and each family will have equal probability of being allocated to MST-CAN or business as usual.

Randomisation will be conducted once a referral has been received and after eligibility has been assessed, informed consent provided, and baseline assessment conducted. The researcher will enter necessary details into an encrypted database and after necessary data has been checked an allocation code will be provided. This code will indicate the nature of allocated group. The researcher will not be able to access randomisation codes in advance of randomisation. The participant will not be blind to the intervention.

Participants

Potential participants will be families with one or more children aged 6 to 17, subject to a Child Protection Plan for neglect, physical and/or emotional abuse in the participating local authority who meet the specified inclusion and exclusion criteria.

Inclusion criteria

- 1. Family has at least one child aged 6-17 years.
- 2. Subject to a Child Protection plan with a report of abuse or neglect in the previous 6 months.

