- 3. Usually resident in the local authority.
- 4. One parent and at least one child willing and able to provide informed consent. Consent will be taken from parents for themselves, and any child aged less than 16 years, children aged 16 years or more will provide their own consent.

Exclusion criteria

1. A child who has already been placed away from home with no prospect of reconciliation.

- 2. A child living independently.
- 3. Current actual or suspected sexual abuse involving family members.
- 4. Primary referral reason is a child's serious mental health issue.
- 5. Referred child assessed as being actively suicidal or homicidal.

Potentially eligible family referred for MST-CAN Family assessed for suitability by MST-CAN team, If ineligible family receive BAU study explained and provided with information sheet If no consent family receive Consent forms signed and BAU referred to evaluation team Evaluation team make contact and conduct baseline assessment Randomised to MST-CAN or BAU Evaluation team inform MST-CAN team and family of the allocation Evaluation team makes contact at 3 months Evaluation team makes contact at 6 months Evaluation team makes contact at 9 months and conducts follow-up assessment

Participant flow through the trial

Sample size

In the pilot study we will recruit 72 participants, 36 in each arm, across the 3 sites, with the expectation that we will successfully follow-up 58 at month 9. This will allow for exploration of key parameters needed to confirm sample size calculation for the efficacy study. It is

sufficient to allow estimation of two-sided 95% CIs around the proportions of eligible, consenting, adhering and followed-up at month 9 in each arm of the study with half-widths less than 0.15. It exceeds the 30 per group recommended by Lancaster et al (Lancaster et al., 2004) and the 35 per group recommended by Teare et al (Teare et al., 2014) for estimating the SE of a primary outcome with sufficient precision, including accounting for any variation across site, where 12 participants per arm per site is recommended.

Outcome measures

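### The cited benchmarks of 30 and 35 per group and 12 per arm per site are met by the families recruited, but not by the 29 families per arm expected at month 9, when the primary outcome is analysed

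*Protocol*

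**What the plan says.** The Sample size section states that "we will recruit 72 participants, 36 in each arm, across the 3 sites, with the expectation that we will successfully follow-up 58 at month 9". It then justifies this size against published guidance. "It exceeds the 30 per group recommended by" one cited methods paper, and it is also said to exceed the 35 per group of a second, simulation-based paper. The stated purpose is "for estimating the SE of a primary outcome with sufficient precision, including accounting for any variation across site". A third figure is given for the site comparison, introduced by the words "where 12 participants per arm per site is recommended".

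The summary table at the front of the protocol gives the unit: "3 sites, 4 local authorities, 72 families". Under Randomisation, "each family will have equal probability of being allocated to MST-CAN or business as usual". Under Primary outcome, the SDQ externalising score relates to the children in the family and is taken at baseline and month 9. Under Data analysis, RQ9, the inferential analysis is of that outcome at month 9.

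**The concern.** The benchmarks are cited for how well the variability of the primary outcome can be estimated. That depends on the number of outcomes observed, and at the time point analysed the paragraph's own attrition figure gives fewer than were recruited. The paragraph compares the benchmarks with the recruited number and does not say that it does so. A reader could take it that the month-9 variability will be estimated from at least 35 per arm and at least 12 per arm per site. On the plan's own expectation, counted in families, it will not.

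At stake is a stated property of the sample size. The pilot is meant to supply parameters for the efficacy trial's sample size, so how precisely the variability will be known should be described correctly. The viability of the pilot is not in question.

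**Working it through.** **Inputs**
- Recruited: 72 in total, 36 per arm, 3 sites (Sample size); the unit is the family (summary table).
- Expected at month 9: 58 (Sample size).
- Allocation: equal probability per family (Randomisation).
- Benchmarks as cited: 30 per group, 35 per group, 12 per arm per site (Sample size).
- Assumptions: equal loss in the two arms, and equal recruitment and loss across sites. The protocol states none of these.

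**Step 1. Reproduce the plan's figures.** 72/2 = 36 per arm and 36/3 = 12 per arm per site. 72 × 0.80 = 57.6, which rounds up to 58 (58/72 = 80.6%). On recruited numbers 36 > 30, 36 > 35, and 12 meets 12 exactly, with nothing in reserve. So the statement is arithmetically right for families recruited.

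**Step 2. Apply the plan's own follow-up.** 58/2 = 29 families per arm; 58/6 = 9.7 per arm per site.

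| Benchmark | Recruited | Expected at month 9 | Shortfall at month 9 |
|---|---|---|---|
| 30 per group | 36 | 29 | 1 |
| 35 per group | 36 | 29 | 6 |
| 12 per arm per site | 12 | 9.7 | 2.3 |

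**Step 3. What the shortfall costs in precision.** I take one outcome per family and a normal outcome, and pool the SD over two arms, with df = 2n − 2. The 95% limits, as multiples of the estimated SD, are √(df/χ²₀.₉₇₅) and √(df/χ²₀.₀₂₅).

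| Families per arm | df | Lower | Upper |
|---|---|---|---|
| 29 | 56 | √(56/78.57) = 0.844 | √(56/37.21) = 1.227 |
| 30 | 58 | 0.847 | 1.222 |
| 35 | 68 | 0.857 | 1.202 |
| 36 | 70 | 0.858 | 1.198 |

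Going from 35 to 29 per arm moves the upper limit from 1.20 to 1.23.

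**Step 4. Several children per family.** The outcome is per child, so 29 families may give more than 29 outcomes. With m children per family and family ICC ρ, the approximate effective number per arm for estimating a variance is 29m/(1 + (m − 1)ρ²). Neither m nor ρ is in the protocol, so the values below are assumptions.
- m = 1: 29.
- m = 1.5: 43.5/1.125 = 38.7 (ρ = 0.5) to 43.5/1.02 = 42.6 (ρ = 0.2).
- m = 2: 58/1.25 = 46.4 (ρ = 0.5) to 58/1.04 = 55.8 (ρ = 0.2).

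The formula for a mean, 29m/(1 + (m − 1)ρ), gives less: 34.8 to 39.5 at m = 1.5, and 38.7 to 48.3 at m = 2.

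**The case against.** The strongest reply is that nothing is miscalculated. The size described is the 72 recruited, every comparison with it is true, and the 58 is disclosed in the same paragraph. Whether the cited benchmarks mean participants recruited or participants with outcome data is settled in sources that are not at hand. The primary outcome is also measured at baseline, before randomisation, when all 36 families per arm should contribute. All of this stands, and it makes the point one of an unstated basis and not of wrong arithmetic. It does not remove the point: the benchmarks are tied to estimating the outcome's variability, the inferential analysis is at month 9, and the text does not limit its claim to recruited or baseline numbers.

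The second reply is that the outcome belongs to children, so 29 is a minimum. This also stands in part. At 1.5 or 2 children per family the effective number for a variance is above 35 in every case worked. But eligibility requires only one child aged 6 to 17, mean family size is something the pilot sets out to estimate (RQ6), and the Sample size section does not use the argument.

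A reader might infer three stronger points that the documents do not support.
- **That the ICC and the pre-post correlation are also declared adequate and fall short.** The benchmarks are cited only for the SE of the primary outcome. The ICC method under RQ6 names no time point and could use baseline data.
- **That the shortfall materially inflates the later trial.** If that trial were planned on an upper one-sided 80% limit, the variance multiplier would be 1.193 at 29 per arm, against 1.189 at 30 and 1.172 at 35. The shortfall accounts for only about 0.3% (1.193/1.189) to 2% (1.193/1.172) of the sample size. Whether to plan on such a limit is a choice for the later trial, not a correction to this one.
- **That the month-9 number falls further, to about 27.6 per arm (0.95 × 58/2), once the 95% completeness mark is applied.** Table 1 does not define the denominator of that criterion.

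**Conclusion.** The point holds as a minor one. The stated adequacy is true of the 36 families per arm recruited or measured at baseline. At the expected month-9 follow-up, counted in families, all three benchmarks are missed: 29 against 30 and 35 per arm, and 9.7 against 12 per arm per site. This rests on equal loss between arms and sites, and on reading the benchmarks as numbers with an observed outcome. The protocol's wording favours that reading, but the sources cannot be checked here. The loss of precision is slight, and with more than one child per family there may be none. No analysis, decision rule or recruitment target needs to change.

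**What to change.** In the Sample size section, replace the comparison with a statement such as: 36 families per arm (12 per arm per site) will be recruited, which meets the cited benchmarks at baseline; about 29 families per arm (about 10 per arm per site) are expected with the month-9 outcome, slightly below them. If the benchmarks are meant for children, state the assumed number of children per family and make the comparison on that basis. Under RQ7, which already promises estimates of precision at each time-point, name the month-9 SD of the primary outcome and its confidence interval explicitly.

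The cost is one or two sentences and a slightly less favourable but accurate justification. No extra families are needed.

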MST-CAN is a licensed, evidence-based intervention working with families with at least one child on a child protection (CP) plan, to reduce risks to children and support safe and effective parenting by addressing underlying barriers. MST-CAN teams include a supervisor, three therapists, a family resource specialist and input from a psychiatrist/nurse to provide an assessment of family mental health needs and support an appropriate treatment plan. Families are referred by their social worker, following a CP conference or legal planning meeting. They are introduced to the service by the MST supervisor and an allocated therapist who will work with them intensively for six to nine months. Therapists meet family members at home to seek both children and adults' views of what they want to change, assess strengths, need, and develop clear safety plans. This then contributes to an analysis of multisystemic factors contributing to abuse and neglect. Goals for treatment are developed in partnership with families and professionals. Sessions take place a minimum of three times weekly, in homes, schools or community settings, with additional contact as needed. Therapists also engage with extended family and friendship networks. An on-call rota provides 24/7 crisis support as needed throughout treatment. The family resource specialist supports families with practical barriers (e.g. finance/housing). Therapy may be individual adult or child-focused, or family-focused, depending on the clinical concern being addressed (individual, family, or community) and the priority concerns for each child and family.

Parents receive parenting and family communications skills training and couples' therapy where appropriate. If anger management is an issue for parents then CBT is provided, for

 $^{^{\}rm 2}$ At this stage the three participating centres are Flintshire and Wrexham, Leeds, and Sandwell .

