General psychological health will be assessed using the short form Depression Anxiety and Stress Scale (DASS-8; (Ali et al., 2022) and emotional regulation using the Difficulties in Emotional Regulation Scale- Short Form (DERS-SF; (Hallion et al., 2018)). Post-traumatic stress symptomology will be assessed using the 20-item, Post-Traumatic Stress Disorder Checklist for DSM-V (PCL-5; (Bovin et al., 2016)). This instrument takes 3 -minutes to complete and has established psychometric properties for the screening of probable PTSD and progression of PTSD symptoms over time.

All child and parent outcomes will be assessed at baseline, prior to randomisation, and again at 9-months post randomisation.

Process measures

Interventions delivered as part of MST-CAN will be derived from weekly case summaries currently completed by staff involved in delivering MST-CAN. Fidelity will be assessed from two perspectives, a parent completed rating of therapists, Child Abuse and Neglect-Therapist Adherence Measure (CAN-TAM), that assesses working relationships and completion of overarching goals and a therapist rating of their supervisor's fidelity (Supervisor Adherence Measure (SAM); www.msti.org/sam) completed every two months that addresses four domains; fidelity to structure and process, adherence to principles of MST-CAN, analytical processes and clinician development.

Table 2: Outcomes and time of assessment

Outcome	No of items	Baseline	Nine months
Child Primary			
Strength and Difficulties (SDQ) ¹	25	✓	✓
Child Secondary			
Wellbeing (KIDSCREEN 10)	10	✓	✓
Psychological Health (RCADS)	25	✓	✓
Post Traumatic Stress Disorder (CRIES-8)	8	✓	✓
Receipt Inventory (CSRI)	6	✓	✓
School Connectedness (SCS)	16	✓	✓
Self-reported delinquency (SRDS) ²	19	✓	✓
Parent Secondary			
Family environment (BFRQ)	16	✓	✓
Psychological Health (DASS-8)	8	✓	✓
Emotional Regulation (DERS-SF)	18	✓	✓
Parent-Child Conflict (CTSPC)	22	✓	✓
Post-Traumatic Stress Disorder (PCL-5)	20	✓	✓
Process measures			
Social Service involvement		✓	✓
Sessions planned and delivered		✓	✓
Supervisor fidelity (SAM)	16	✓	✓
Therapist adherence (CAN-TAM)	18	✓	~

¹We will compare the SDQ collected from three sources; parent, practitioner and school. ²This will be collected for children and young people aged 10 or more years at baseline

Methods and data collection

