RQ11 - Fidelity in the MST-CAN group will be assessed from two perspectives, a parent completed rating of therapists, CAN-TAM, that assesses working relationships and completion of overarching goals, and a supervisor rating of fidelity (SAM) completed every two months that addresses four domains; fidelity to structure and process, adherence to principles of MST-CAN, analytical processes, and clinician development. We will present mean scores and 95% confidence intervals for each outcome at each time-point to provide an estimate of intervention fidelity.

Implementation and process evaluation

Research objectives.

A qualitative analysis will be used to address key objectives addressing the implementation, process and equity associated with the pilot. This will focus on assessing the extent to which the intervention has been implemented as intended including factors that facilitate or hinder implementation, the acceptability of the intervention from the perspectives of participants, staff and families and identify positive and negative experiences associated with the intervention and when they occur.

Research questions.

- **IPEQ1** To qualitatively explore BAU across each site.
- **IPEQ2** To qualitatively explore barriers, acceptability, implementation, and retention from the perspective of participants, practitioners, and stakeholders.
- **IPEQ3** To qualitatively explore issues relating to equality, diversity, and inclusion from the perspectives of participants, practitioners, and stakeholders.

Table 3: IPE methods overview

IPE methods overview

IPE Question	Data collection methods	Participants/ data sources (type, number)	Data analysis methods	Research questions addressed	Implementation / logic model relevance
BAU Control (IPE Q1)	Qualitative interviews with relevant stakeholders (i.e., service leads, social workers)	10-15 semi- structured interviews with stakeholders. Purposive sampling to obtain variety by site, gender identity, ethnicity	Transcription and inductive analysis to allow themes to emerge naturally	Explore the nature of and variation in BAU across local authorities	Identify what the comparison control group interventions are comprised of

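### Table 2 times the parent-rated fidelity measure (CAN-TAM) before randomisation and at month 9, with no clear point during treatment, and conflicts with the text on SAM and session data

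*Protocol*

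**What the plan says.** In the Protocol's Outcome measures section, "Table 2: Outcomes and time of assessment" has two timing columns, baseline and nine months. Three of its process rows matter here: "Therapist adherence (CAN-TAM" (18 items), "Supervisor fidelity (SAM" (16 items) and "Sessions planned and delivered". All three are marked in both columns. The odd character in the CAN-TAM nine-month cell is taken to be a tick misread from the PDF.

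The Randomisation section places the baseline assessment before allocation, and the participant flow has the MST-CAN team told of the allocation only afterwards. The Intervention section says that a family has an allocated therapist "who will work with them intensively for six to nine months".

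The Process measures section describes CAN-TAM as the parent's rating of the therapist and SAM as the therapist's rating of the supervisor, "completed every two months that addresses four domains". Interventions delivered are taken from weekly case summaries, and the Data analysis section repeats this under RQ10. Under RQ11 the second measure becomes "a supervisor rating of fidelity (SAM) completed every two months", and the analysis is: "We will present mean scores and 95% confidence intervals for each outcome at each time-point". RQ11 does not say which time-points these are.

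**The concern.** CAN-TAM asks a parent about the working relationship with a therapist and about goals completed. Before randomisation there is nothing to rate. At month 9 many courses may already have finished. Neither point in Table 2 is clearly inside treatment, and the text gives CAN-TAM no separate interval. The Methods and data collection section supports the table's timing, since it collects quantitative data from parents before randomisation and at nine months.

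At stake is the parent's half of the fidelity evidence in RQ11, which also feeds the revised theory of change. Ratings not taken while treatment is running cannot be recovered in analysis, so a later analysis plan cannot repair this. For SAM and sessions the risk is smaller: staff working from Table 2 would collect data on a different schedule from staff working from the text.

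**Working it through.** The plan states no figure to reproduce. The check counts how many scheduled assessments fall inside treatment.

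**Inputs.** Table 2: CAN-TAM at baseline and month 9. Randomisation section: baseline precedes allocation. Intervention section: course length L of 6 to 9 months. Sample size section: 36 families per arm, with 58 of 72 expected at month 9. Process measures and RQ11: SAM every two months. Process measures and RQ10: weekly case summaries. The Protocol gives neither the lag d from randomisation to the start of treatment nor the distribution of L, so d is an assumption.

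**CAN-TAM, baseline.** No family has been allocated, so 0 of 36 MST-CAN families can give a usable rating.

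**CAN-TAM, month 9.** Treatment ends at month L + d.
- With d = 0 it ends between month 6 and month 9. Month 9 is then 9 − 9 = 0 to 9 − 6 = 3 months after the end, and no rating falls strictly within treatment.
- With a delay, month 9 is inside treatment only if L > 9 − d. For d = 1 that means courses longer than 8 months, and for d = 2 longer than 7 months. A six-month course is still running at month 9 only if d exceeds 3 months.

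**Number of ratings.** Planned follow-up is 58/72 = 0.806, about 80%. In the MST-CAN arm, 0.80 × 36 = 28.8, or about 29 families, each with one rating.

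**SAM under the text.** In a six-month course: months 2, 4 and 6, so about 3 ratings. In a nine-month course: months 2, 4, 6 and 8, so about 4. Table 2 shows neither pattern.

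**Case summaries under the text.** 6 × 52/12 = 26 weekly records for a six-month course and 9 × 52/12 = 39 for a nine-month course. Table 2 shows two ticks, one of them before any session could be delivered in the trial.

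**Knock-on effect, conditional.** RQ8 questions any outcome with more than 40% missing at a time-point, and RQ2 includes the completeness of process outcomes. If those rules are applied to CAN-TAM as Table 2 schedules it, the measure is 100% missing at baseline by construction. At month 9 it is at least 36/72 = 50% missing if all 72 families form the denominator, because business-as-usual families have no MST-CAN therapist.

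**The case against.** The strongest reply is that the text already provides for measurement during treatment. SAM is set at every two months in two places, and delivery data come from weekly records. A reader of Table 2 alone might infer that fidelity as a whole goes unmeasured during treatment. The documents do not support that. SAM is a therapist's rating of the supervisor and does not depend on a family having a therapist, and the sessions data serve RQ10 and not RQ11. For these two rows only the contradiction stands.

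For CAN-TAM, it can be argued that the two-monthly phrase in the Process measures section covers both instruments, since they share a sentence. The phrase most naturally attaches to SAM, and in RQ11 a comma closes the CAN-TAM clause before SAM is introduced. At best the timing is unclear.

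A reader might also infer that fidelity would be overstated because families who leave treatment early are missed. That is plausible but not shown. The Ethics and registration section lets families stop the intervention and still give follow-up data, and nothing in the Protocol gives the size or direction of any bias. Nor does it follow that the pilot could not tell weak delivery from a weak programme: SAM, the case summaries and the implementation interviews, including 5 to 10 with parents who dropped out, all bear on delivery. Counting two-monthly SAM rounds over the whole delivery window and setting them against one tick would also mislead, because Table 2 is a per-family schedule.

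Fidelity is not a progression criterion in Table 1, which limits the consequence. The different descriptions of the SAM rater may be only loose wording, since a supervisor rating can mean a rating of the supervisor.

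**Conclusion.** The point holds for CAN-TAM. As scheduled, the baseline rating cannot exist, and the only usable one comes from about 29 of 36 families. If treatment starts near randomisation, that rating comes 0 to 3 months after a six-to-nine-month course ends. A delayed start would bring some of the longer courses back inside month 9, but the Protocol states no lag. No CAN-TAM time-point within treatment is clearly given, so the parent-rated half of RQ11 is badly fixed.

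For SAM and sessions the finding is only that Table 2 contradicts the text and must be reconciled with it. No claim is made that fidelity overall is unmeasured or overstated. The correction should be made before data collection because the lost ratings cannot be reconstructed.

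**What to change.** In Table 2, remove the baseline ticks for CAN-TAM, SAM and sessions, and mark these rows as MST-CAN arm, during treatment. Then:
- State CAN-TAM points within treatment, for example at the research contacts already planned for months 3 and 6, as well as month 9.
- Keep SAM at every two months and sessions from the weekly case summaries, as the text has them.
- Define RQ11's time-points as these CAN-TAM and SAM ratings.
- Describe the SAM rater in the same way under Process measures and under RQ11.

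The cost is a table correction, a sentence or two of text, and one or two extra 18-item forms per MST-CAN family. With months 3 and 6 added and the baseline form dropped, a family has three occasions against the two in Table 2. Asking about the therapist at these contacts reveals nothing new to the evaluation team, which already informs families of their allocation.
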